8.4.3 Visit 3 (Week 1 ± 2 days)

- Record concomitant medications
- Collect and review Subject Daily Diary for Artificial Tear Use (as needed)
- Record AEs
- VAS Frequency and Severity for Eye Dryness
- OSDI
- SPEED assessment
- BCVA assessment
- Slit lamp biomicroscopy, including punctum assessment
- Investigator Rated Conjunctival Hyperemia Grade
- CFS
- OTX-DED or HV Insert Presence by visual assessment
- Ease of Visualization by Investigator ([Appendix 12](#))
- Tear Film PK by Schirmer
- IOP
- Dispense artificial tears and diary (as needed)

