4.2 Investigational Product Rationale

[figure not shown]
Given limitations of topical ocular treatments and devices indicated for treatments of DED, there is a rational for novel therapies. Ocular Therapeutix has designed a resorbable intracanalicular insert as the platform for drug delivery products which can be used to deliver various active pharmaceutical ingredients approved by the Food and Drug Administration (FDA).

OTX-DED is an intracanalicular insert that consists of two main components: dexamethasone and polyethylene glycol (PEG) based hydrogel conjugated with fluorescein. OTX-DED contains approximately 0.2 mg or 0.3 mg of dexamethasone and is designed to provide a sustained and tapered release of dexamethasone for up to 14 and 21 days, respectively. Over this time and through hydrolysis, OTX-DED softens, liquefies and is cleared through the nasolacrimal duct without the need for removal. The fluorescent PEG illuminates when excited with a blue light source to allow for visualization of product presence.

Figure 1 Dexamethasone Entrapped in the Hydrogel Intracanalicular Insert

Name	Dry Dimensions	Hydrated Dimensions
OTX-DED 0.2mg Dexamethasone Ophthalmic Insert	Diameter: 0.41-0.49mm Length: 2.14-2.36 mm	Diameter: 1.35-1.80mm Length: 1.8mm
OTX-DED 0.3mg Dexamethasone Ophthalmic Insert	Diameter: 0.44-0.55mm Length: 2.14-2.36mm	Diameter: 1.35-1.80 mm Length: 1.8mm
Hydrogel Vehicle (HV) Insert	Diameter: 0.38mm Length: 2.25mm	Diameter: 1.5 mm Length: 1.8mm

The insert is designed to be placed in the inferior or superior punctum and is retained in the canaliculus for the entire duration in which the drug is being delivered. Over time the insert softens and liquefies via hydrolysis, resulting in clearance through the nasolacrimal duct.

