8.4 Study Assessments by Visit

Perform study procedures as referenced in the Schedule of Events ([Appendix 1](#)) in the order specified below. Note: All subjects will have both eyes evaluated at all visits.

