8.4.1 Visit 1 (14 ±2 days prior to Day 1) Screening/Baseline Visit

Note: The Screening Visit can be split into two (2) visits in rare cases, but both visits must be within the allowable window.

- Informed consent
- Demographics
- Medical/ophthalmic history
- Record concomitant medications
- VAS Severity and Frequency for Eye Dryness ([Appendix 2](#))
- OSDI ([Appendix 3](#))

- SPEED assessment ([Appendix 4](#))
- BCVA assessment ([Appendix 8](#))
- Slit lamp biomicroscopy (including punctum assessment) ([Appendix 9](#))
- Investigator Rated Assessment of Bulbar Conjunctival Hyperemia ([Appendix 5](#))
- CFS ([Appendix 7](#))
Note: Wait 15 minutes prior to conducting unanesthetized Schirmer test
- Unanesthetized Schirmer
- IOP
- Dilated fundus exam
- Determine Eligibility
- Dispense artificial tears (as needed and not to be administered within 2 hours of clinic visit.)
- Dispense Daily Subject Diary for Artificial Tear Use (as needed) ([Appendix 14](#))

8.4.2 Visit 2 Insertion/Day 1

- Record concomitant medications
- Record AEs*
Note: Any signs, symptoms or conditions captured prior to the insertion of IP, will be recorded as medical history.
- Collect and review Subject Daily Diary for Artificial Tear Use (if applicable)
Note: Subjects using rescue AT > 3x/day for 3 consecutive days will be ineligible for randomization.
- VAS Frequency and Severity for Eye Dryness
- OSDI
- SPEED assessment
- Conjunctival Hyperemia Photography ([Appendix 6](#))
- BCVA assessment
- Slit lamp biomicroscopy, including punctum evaluation
- Investigator Rated Assessment of Bulbar Conjunctival Hyperemia
- CFS
- IOP
- Punctum Size Assessment
- Urine pregnancy test (if applicable must be performed prior to treatment)
- Determine Eligibility for Insertion
- Randomization
- OTX-DED or HV Insert Placement ([Appendix 11](#))*

Note: If placement is only successful in one eye, the items with the asterisk should be performed on the same day. Subjects should be asked to return within 0-3 days to attempt insertion in the other eye. At the return visit, items with an asterisk should be performed on the second eye, and the AE review, Ease of Insertion Assessment and Tear film PK for the second eye should only be performed if the second eye has a successful insertion.

- Ease of Insertion Assessment*
- Tear film PK by Schirmer (to be collected 1 hour (\pm 30 minutes), 2 hours (\pm 30 minutes) and 4 hours (\pm 30 minutes) post-insertion)* ([Appendix 10](#))

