Appendix 1 Time and Events Schedule

See [Section 8.4](#) for order of assessments.

Study Parameter	Screening/ Baseline Visit Day -14 (-16 to -12)	Insertion Day 1	Follow-up Day 8 Week 1 ±2 days	Follow-up Day 15 Week 2 ±2 days	Follow-up Day 22 Week 3 ±2 days	Follow-up Day 29 Week 4 ⁶ ±3 days	Follow-Up Day 57 Week 8 (± 10 days)
Visit	1	2	3	4	5	6	7
Informed Consent	X						
Determine Eligibility	X	X					
Demographic Information	X						
Medical/Ophthalmic History	X						
Record Medications	X	X	X	X	X	X	X
Record Adverse Events ^{3,7}		X	X	X	X	X	X
Urine Pregnancy Test ¹		X					X
VAS for Eye Dryness	X	X	X	X	X	X	X
OSDI	X	X	X	X	X	X	X
SPEED	X	X	X	X	X	X	X
Conjunctival Hyperemia photography		X		X			
Assessment of BCVA	X	X	X	X	X	X	X
Slit Lamp Biomicroscopy (including punctum assessment)	X	X	X	X	X	X	X
Investigator Rated Conjunctival Hyperemia grade	X	X	X	X	X	X	X
Corneal Fluorescein Staining Using the NEI Scale	X	X	X	X	X	X	X
OTX-DED or HV Insert Presence by Visual Assessment			X	X	X	X	X
Ease of Visualization as assessed by Investigator			X	X	X	X	X
Unanesthetized Schirmer Tear Test	X						
Tear Film PK performed using Schirmer Strips ^{3,4,5}		X	X	X	X	X	X
IOP Measurement	X	X	X	X	X	X	X
Fundus Exam ²	X						X
Punctum Size Assessment		X					X
Randomization		X					
OTX-DED or HV Insert Placement ³		X					
Ease of Insertion as assessed by the Investigator ³		X					
Dispense Sponsor Supplied Artificial Tears (if needed) and Daily Diary	X	X	X	X	X	X	
Collect/review Daily Subject Diary for Artificial Tear Use (as needed)		X	X	X	X	X	X

¹ A negative UPT is required for women of childbearing age to be included in the study.

- 2 Dilated fundus examination at screening; undilated fundus examination at Week 8.
- 3 Prior to insertion, a clinical determination of the absence of infection will be made based on the lack of erythema or discharge at the punctum. If placement is only successful in one eye, subjects should be asked to return within 1-3 days to attempt insertion in the other eye. The following items should be repeated at the return visit, Insert Placement, Ease of Insertion, Tear Film PK and AEs.
- 4 Tear Film PK will be collected at 1 hour (± 30 minutes), 2 hours (± 30 minutes), and 4 hours (± 30 minutes) post insertion on Day 1. Tear Film PK should be collected using Schirmer strips.
- 5 Tear Film PK will be collected using Schirmer Tests strips. These will be collected and sent to the central lab for analysis. See lab manual.

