Appendix 7 Corneal Fluorescein Staining (CFS) Procedure - Using NEI Scale

CFS may be completed right eye first followed by the left eye. Using this technique only one fluorescein strip is required to apply the dye to both the right and left eye.

1. Wet a sponsor supplied Fluorescein strip with the sponsor supplied saline solution/eye wash. Use enough liquid to wet the end of the strip without liquid falling from the end of the strip.
2. Ask the subject to look up and touch the moistened strip to the inferior palpebral conjunctiva without touching the strip to the bulbar conjunctiva.
3. Ask the subject to blink several times to distribute the fluorescein dye.
4. Wait between 2 to 3 minutes before evaluating the cornea for staining.
5. Use the cobalt blue illumination and the Wratten yellow filter to assess the corneal staining.
6. Record the staining for each of the 5 regions of the cornea, central, inferior, nasal, temporal, and superior using the NEI 0-3 scoring scale (see diagram). The CFS total score will be the sum of the five areas (0 to 15).

Grade each region, Central (1), Superior (2), Temporal (3), Nasal (4), Inferior (5), for each eye according to the following grading scale:

[figure not shown]
0 = No Staining

1 = Mild Staining

2 = Moderate Staining

3 = Severe Staining

NEI Corneal Staining Grading - Scale

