Appendix 12 OTX-DED or HV Insert Ease of Visualization

The Investigator will assess the presence of OTX-DED or HV insert at each study visit, using a blue light and yellow filter. The Investigator will be asked to grade the level of ease of visualization of the punctum plug as “easy”, “moderate”, or “difficult”.

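### Insert presence and ease of visualization are read after fluorescein is instilled for corneal staining, under the same type of light and filter, so residual dye could cause them to be misread

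*Protocol*

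**What the plan says.** **Order.** Protocol Section 8.4 makes the sequence of each visit list binding ("in the order specified below. Note: All subjects will have both eyes evaluated at all visits"). The Time and Events Schedule in Appendix 1 sends the reader back to Section 8.4 "for order of assessments". In the lists for Visits 3 to 7, the item "OTX-DED or HV Insert Presence by visual assessment" stands after CFS.

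**The dye.** In Appendix 7 a moistened fluorescein strip is touched to the inferior palpebral conjunctiva, the subject blinks to spread the dye, and the cornea is read after 2 to 3 minutes: "Use the cobalt blue illumination and the Wratten yellow filter to assess the corneal staining".

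**The insert.** Protocol Section 4.2 describes OTX-DED as a hydrogel conjugated with fluorescein and says: "The fluorescent PEG illuminates when excited with a blue light source to allow for visualization of product presence". Appendix 11 places the insert slightly below the punctal opening. It says that both OTX-DED and HV inserts can be seen under blue light with a yellow filter. Appendix 12 has the investigator assess presence at each visit "using a blue light and yellow filter" and grade ease of visualization as easy, moderate or difficult.

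**Uses of the readings.** Presence and ease of visualization are exploratory endpoints (Protocol 6.2.2.2). SAP 4.7.4 compares presence between arms by Fisher's exact test with 95% confidence intervals, and ease of visualization by Pearson chi-squared. SAP 4.6 derives exposure duration from the dates on which the insert is found absent. The protocol synopsis gives the check for the insert as the reason for following subjects to Week 8.

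**The concern.** The dye used for CFS and the marker in the insert are both fluorescein. They are viewed with the same type of light and filter, at neighbouring sites, within one visit, and the dye goes in first. Residual dye at the punctum could make a cleared insert look present. It could also hide a faint insert, or change how easy the insert seems to find.

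What is at stake is the quality of the retention data. The sample size section says that the trial is meant to supply initial estimates for later designs. Misread presence would bias the retention estimate in each arm, weaken the comparison between arms, and could alter the exposure summary. The problem is avoidable, because the order of two items in a list creates it.

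**Working it through.** The plan states no rate or power for insert presence, so there is no figure to reproduce. The check is mainly textual.

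**1. Position of the insert check (Protocol 8.4.3 to 8.4.7)**

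| Visit | Steps between CFS and insert presence | Rinse or wait listed |
|---|---|---|
| 3, 4, 5, 6 | none | none |
| 7 | undilated fundus examination | none |

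Ease of visualization follows presence at all five visits. The 2 to 3 minutes in Appendix 7 is the delay before the cornea is read, not time for the dye to clear. The only wait after CFS in any visit list is at Visit 1 ("Wait 15 minutes prior to conducting unanesthetized Schirmer test"), where no insert is in place.

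**2. Is presence recorded before the dye?** Slit-lamp biomicroscopy with punctum assessment precedes CFS at Visits 3 to 7. Appendix 9 lists eyelids including punctum size, and SAP 2.6.2 lists punctal appearance among the slit-lamp variables. Neither lists insert presence. The recorded presence reading is the one made after the dye.

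**3. Number of readings.** The scheduled maximum is 5 visits × 300 eyes = 1,500 presence readings. This is a ceiling on opportunities, not a count of errors. A false present can occur only in an eye that has lost its insert, and a false absent only in an eye that still has one. The documents give neither number.

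**4. Exposure duration (SAP 4.6).** Exposure = date of confirmed absence − date of earliest insertion + 1. Assume insertion on Day 1 and visits on their nominal days.

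- If the date means the first visit at which absence is established (for the later eye), one false present at that visit moves the result by one visit interval. From Day 15 to Day 22 this is (22 − 1 + 1) − (15 − 1 + 1) = 7 days. From Day 29 to Day 57 it is 57 − 29 = 28 days.
- If the date means the last visit at which absence was recorded, a subject clear from Day 15, misread at Day 15 and read correctly on Days 22, 29 and 57 has 57 days either way. The shift is 0. Under this reading only a misreading at the last visit matters: a false present at Day 57 would leave Day 29 as the last confirmed absence, 28 days shorter.

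The SAP wording does not settle which is meant.

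**5. Effect on the comparison between arms (illustration only).** The true proportions and error rates here are assumptions; none comes from the documents. With true presence p, false-positive rate fp and false-negative rate fn, the same in both arms:

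observed proportion = p(1 − fn) + (1 − p)fp, so observed difference = true difference × (1 − fn − fp).

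For p = 0.40 and 0.70, fp = 0.10 and fn = 0, the observed values are 0.40 + 0.60 × 0.10 = 0.46 and 0.70 + 0.30 × 0.10 = 0.73, a difference of 0.27. Power uses the normal approximation for two proportions, with 50 subjects per arm and two-sided alpha 0.05.

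| Assumed fp (fn = 0) | True 40% vs 70%: difference, power | True 10% vs 30%: difference, power |
|---|---|---|
| 0 | 30 points, 0.87 | 20 points, 0.71 |
| 0.10 | 27 points, 0.79 | 18 points, 0.52 |
| 0.20 | 24 points, 0.71 | 16 points, 0.38 |
| 0.30 | 21 points, 0.62 | 14 points, 0.29 |

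The table shows direction only: equal error rates shrink the difference and favour no arm, while false positives inflate the retention estimate in every arm.

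**6. Primary endpoint.** At Visit 4 hyperemia photography is listed before CFS, so the Day 15 photographs are taken before that visit's dye.

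**The case against.** The strongest objection is that no passage says free dye mimics or hides the insert. The insert is a discrete body, 1.35 to 1.80 mm wide and 1.8 mm long once hydrated for OTX-DED. Investigators are trained on Instructions for Use that are not among the documents. All arms follow the same order under masking, and the affected items are exploratory or descriptive in a trial that is not powered for significance. All of this stands. It limits the weight of the point but does not explain why the reading should follow the dye.

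A second objection concerns the remedy. If insert status were recorded with the slit-lamp examination, it would come before two subjective secondary endpoints, the investigator hyperemia grade and CFS. That is a fair reason to place the insert items after the hyperemia grade. Only CFS would then follow them, and the punctum has by then already been examined at the slit lamp.

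Several stronger readings are tempting but unsupported:

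- **That fluorescence is the only way to recognise the insert.** The protocol says that it allows visualization, not that it is the sole cue. Appendix 13 has the insert identified through the punctal tissue before removal.
- **That the 15-minute wait at Visit 1 shows the sponsor recognised dye carry-over.** No reason is given for it, and added fluid or reflex tearing before a Schirmer test would explain it equally well.
- **That tear PK samples are compromised.** The strips do follow CFS at Visits 3 to 7, but the documents state no effect on the assay, and the procedure is in a laboratory manual that is not included.

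**Conclusion.** The point holds as an avoidable risk of misclassification. The order, the shared dye, the matching type of light and filter, the adjacent site and the absence of a rinse or wait are all in the text. That misreading follows from them is an inference, and its frequency is unknown.

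The reach is narrow: presence and ease of visualization as exploratory endpoints, the exposure duration in SAP 4.6, and the Week 8 check for the insert. A reader might infer that 1,500 readings are in error or that exposure is off by 7 or 28 days. The first figure is only a ceiling, and the second depends on an unsettled reading of the SAP definition. The primary endpoint and its analysis are untouched. The change is worth making because it is cheap, not because the damage is shown to be large.

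**What to change.** In Protocol 8.4.3 to 8.4.7, list Insert Presence and Ease of Visualization after the investigator hyperemia grade and immediately before CFS. Leave the rest of the order as it is.

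This moves two lines in five visit lists and adds no procedure. The one downside is that insert status is recorded before CFS is scored.

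If the visits are already complete, state in the study report that presence and ease of visualization were read after dye instillation, and interpret the retention and exposure results with that in mind.

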8.4.4 Visit 4 (Week 2 ± 2 days)

- Record concomitant medications
- Collect and review Subject Daily Diary for Artificial Tear Use (as needed)
- Record AEs
- VAS Frequency and Severity for Eye Dryness
- OSDI
- SPEED assessment
- Conjunctival Hyperemia Photography
- BCVA assessment
- Slit lamp biomicroscopy, including punctum assessment
- Investigator Rated Conjunctival Hyperemia Grade
- CFS
- OTX-DED or HV Insert Presence by visual assessment
- Ease of Visualization by Investigator
- Tear Film PK by Schirmer
- IOP
- Dispense artificial tears and diary (as needed)

8.4.5 Visit 5 (Week 3 ± 2 days)

- Record concomitant medications
- Collect and review Subject Daily Diary for Artificial Tear Use (as needed)
- Record AEs
- VAS Frequency and Severity for Eye Dryness
- OSDI
- SPEED assessment
- BCVA assessment
- Slit lamp biomicroscopy, including punctum assessment
- Investigator Rated Conjunctival Hyperemia Grade
- CFS
- OTX-DED or HV Insert Presence by visual assessment

- Ease of Visualization by Investigator
- Tear Film PK by Schirmer
- IOP
- Dispense artificial tears and diary (as needed)

8.4.6 Visit 6 (Week 4 ±3 days)

- Record concomitant medications
- Collect and review Subject Daily Diary for Artificial Tear Use (as needed)
- Record AEs
- OSDI
- VAS Frequency and Severity for Eye Dryness
- SPEED assessment
- BCVA assessment
- Slit lamp biomicroscopy, including punctum assessment
- Investigator Rated Conjunctival Hyperemia Grade
- CFS
- OTX-DED or HV Insert Presence by visual assessment
- Ease of Visualization by Investigator
- Tear Film PK by Schirmer
- IOP
- Dispense artificial tears and diary (as needed)

8.4.7 Final Visit 7 (Week 8±10 days)

- Record concomitant medications
- Collect and review Subject Daily Diary for Artificial Tear Use (as needed)
- Record AEs
- Urine Pregnancy Test
- VAS Frequency and Severity for Eye Dryness
- OSDI
- SPEED assessment
- BCVA assessment
- Slit lamp biomicroscopy, including punctum assessment
- Investigator Rated Conjunctival Hyperemia Grade
- CFS
- Undilated Fundus Exam
- OTX-DED or HV Insert Presence by visual assessment
- Ease of Visualization by Investigator
- Tear Film PK by Schirmer
- IOP
- Punctum Size Assessment

8.4.8 Unscheduled Visits

An unscheduled visit may be performed during the course of the trial in order to ensure subject safety. All procedures performed at an unscheduled visit will be recorded in the source documents and on the Unscheduled Visit eCRF pages.

Evaluations that may be conducted at an Unscheduled Visit may include:

- BCVA assessment

- Slit lamp biomicroscopy
- IOP
- Dilated or Undilated fundus exam
- Urine pregnancy test (if applicable)
- Assessment of AEs
- Assessment of concomitant medications and/or treatments
- Any other assessments needed in the judgment of the investigator

9 ADVERSE EVENTS

The investigator and study staff are responsible for detecting and recording AEs and SAEs, during scheduled safety evaluations and whenever such information is brought to their attention.

This section of the protocol provides definitions and detailed procedures to be followed.

During each visit, the Investigator will question the subject about adverse events using an open question taking care not to influence the subject's answers. Throughout the course of the study, every effort must be made to remain alert to possible AEs. If an AE occurs, the first concern should be for the safety of the subject. If necessary, appropriate medical intervention should be provided. At the signing of the ICF, each subject must be given the names and telephone numbers of study site staff for reporting AEs and medical emergencies.

9.1 Definition of an Adverse Event

An AE is any untoward medical occurrence in a patient or clinical investigation subject administered a pharmaceutical product and that does not necessarily have a causal relationship with this treatment. An AE can therefore be any unfavorable and unintended sign (including an abnormal laboratory finding), symptom, or disease temporally associated with the use of a medicinal (investigational) product, whether or not related to the medicinal (investigational) product. Examples of an AE include:

- Exacerbation of a pre-existing condition including either an increase in frequency and/or intensity of the condition
- New conditions detected or diagnosed after IP administration even though it may have been present prior to the start of the study.
- Signs, symptoms of a drug interaction
- Signs, symptoms of a suspected overdose of either IP or a concurrent medication (overdose per se should not be reported as an AE/SAE).
- A laboratory abnormality occurring after the start of the study (i.e., after screening) that results in subject withdrawal from the study or medical treatment or further follow-up.

9.2 Definition of Serious Adverse Event

An SAE is any untoward medical occurrence that at any dose:

- Results in death
- Is life-threatening

Note: The term "life-threatening" refers to an event in which the subject was at risk of death at the time of the event; it does not refer to an event which hypothetically might have caused death if it were more severe.

- Requires in-patient hospitalization or prolongation of existing hospitalization. Hospitalizations for elective surgeries do not constitute an SAE.
- Results in persistent or significant disability/incapacity.
- Is a congenital abnormality/birth defect.

Medical and scientific judgment should be exercised in deciding whether other situations should be considered SAEs, such as important medical events that might not be immediately life threatening or result in death or hospitalization but might jeopardize the subject or might require intervention to prevent one of the other outcomes listed above.

